A SAFETY TRIAL OF DANTROLENE SODIUM IN PEDIATRIC AND ADULT PATIENTS WITH WOLFRAM SYNDROME

Study Phase: Phase 1b

Product name: Dantrolene Sodium

Indication: Wolfram syndrome

Sponsor: Washington University School of Medicine

Sponsor contact: [name]

IRB ID #: 201607006

FDA IND #: 133439

Protocol synopsis

Title	A Safety Trial of Dantrolene Sodium in Pediatric and Adult Patients with Wolfram Syndrome.
Protocol number	
Investigational product	Dantrolene Sodium for oral administration
Study objectives	
The Primary Objective of this study is: To assess the safety and tolerability of dantrolene sodium administered orally at upper end of therapeutic dose range for 6 months in patients with Wolfram syndrome with an optional extension phase up to 24 months. Patients who express the wish to continue in the optional extension phase on dantrolene sodium will be offered this possibility.
 
The Secondary Objectives of this study are:
 
• Determine the effect of dantrolene sodium on remaining beta cell functions using a mixed-meal tolerance test and monitoring base-line C-peptide levels, blood glucose levels, proinsulin/C-peptide ratios, hemoglobin A1c levels, and urine glucose levels.• To determine the efficacy of dantrolene sodium on visual acuity (LogMar scores)• To determine the efficacy of dantrolene sodium on visual functions using Visual Functioning Questionnaire – 25.• To evaluate the efficacy of dantrolene sodium on neurological functions using the Wolfram Unified Rating Scale (WURS) and standard neurological assessments. 
The Exploratory Objectives of this study are:
 
• To further explore potential relationships between predefined biomarkers and endocrine and neurological symptoms, including serum levels of mesencephalic

	
astrocyte-derived neurotrophic factor (MANF), myelin basic proteins, and circulating insulin DNA.
 
 • To evaluate the effects of dantrolene sodium on functional activities of daily living by assessing health related quality of life using PedsQL (pediatric patients) and SF-36v2 (adult patients).
Study endpoints	
The Primary Endpoint of this study is:
 
 • To assess the safety and tolerability of dantrolene sodium administered orally up to 100 mg b.i.d. (adults) and up to 2 mg/kg b.i.d. (pediatric patients, up to 50 kg) for 6 months with an optional extension phase up to 24 months in patients with Wolfram syndrome. • Safety will be assessed by adverse events (by type and severity) and changes in clinical laboratory testing (including liver function tests). • This will be assessed by monitoring of serum chemistry including liver function tests and ammonia. • Safety will be also assessed by complete physical exam (PE), vital signs (vs)/weight (wt) at each visit 
The Secondary Endpoints include:
 
 • Determine the effect of dantrolene sodium on remaining beta cell functions using a mixed-meal tolerance test and monitoring base-line C-peptide levels, blood glucose levels, proinsulin/C-peptide ratios, hemoglobin A1c levels, and urine glucose levels. • To determine the efficacy of dantrolene sodium on visual acuity (LogMar scores) • To determine the efficacy of dantrolene dosicum on visual functions using Visual Functioning Questionnaire – 25. • To evaluate the efficacy of dantrolene sodium on neurological functions using the Wolfram Unified Rating Scale (WURS) and standard neurological assessments.
Inclusion criteria	
Patients must meet all of the following criteria to be eligible for enrolment:
 
 1. The patient has a definitive diagnosis of Wolfram syndrome, as determined by the following: 
 a. Documented functionally relevant recessive mutations on both alleles of the WFS1 gene or dominant mutation on one allele of the WFS1 gene based on historical test results (if available) or from a qualified laboratory at screening. 2. The patient is at least 5 years of age (biological age) at the time of written informed consent. 3. The patient, patient's parent(s), or legally authorized guardian(s) must have voluntarily signed an Institutional Review Board/Independent Ethics Committee-approved

	
informed consent form after all relevant aspects of the study have been explained and discussed with the patient. The guardians' consent and patient's assent, as relevant, must be obtained.

Exclusion criteria	
Patients who meet any of the following criteria are not eligible for this study:
 
 1. The patient has clinically significant non-Wolfram related CNS involvement which is judged by the investigator to be likely to interfere with the accurate administration and interpretation of protocol assessments. 2. The patient has a known defect in oxidative phosphorylation (such as a confirmed mitochondrial myopathy) 3. The patient has abnormal liver function (defined as serum transaminases more than twice the upper limit of normal for the reference laboratory) 4. The patient has a significant medical or psychiatric co-morbidity that might affect study data or confound the integrity of study results. 5. The patient has received treatment with any investigational drug within the 30 days prior to study entry. 6. The patient has received blood product transfusions within 90 days prior to screening. 7. The patient is unable to comply with the protocol, (e.g. has a clinically relevant medical condition making implementation of the protocol difficult, unstable social situation, known clinically significant psychiatric/behavioral instability, is unable to return for safety evaluations, or is otherwise unlikely to complete the study), as determined by the Investigator. 8. The patient has a known history of central apnea and/or ventilation requirements. 9. The patient has a known history of chronic obstructive pulmonary disease, pleural effusion, and/or myocardial disease.
Number of patients planned and duration of study participation	
Up to 50 patients (25 adults and 25 children) will be enrolled to provide a total of a) 46 evaluable patients who complete the study (23 adults and 23 children), based on an anticipated drop-out rate of 10%;
 
The planned duration of oral dantrolene sodium administration in this study is 6 months with an optional extension phase up to 24 month. The planned overall duration of each patient's participation in this study is 9 months. For participants who continue in the optional extension phase, the planned overall duration is up to 27 months (screening, study drug dose maximization, outcome measure evaluation, and final safety follow-up).

Treatment administered and treatment schedule	
Patients who receive study drug will undergo a run-in period (3 weeks) for dose maximization.
 
Adults

	
Up to 25 mg once daily for seven days as prescribed by the physician, then Up to 25 mg b.i.d. for seven days Up to 50 mg b.i.d. for seven days Up to 100 mg b.i.d.
 
Pediatric Patients (a patient with an age < 18 years) up to 50 kg Up to 0.5 mg/kg once daily for seven days as prescribed by the physician, then Up to 0.5 mg/kg b.i.d. for seven days Up to 1 mg/kg b.i.d. for seven days Up to 2 mg/kg b.i.d.
 
No dose changes if weight change is within $\pm 3\%$ of the original dosing weight.
 
Dantrolene sodium for oral use will be provided by the Washington University's clinical trials pharmacy

Study duration	The duration of this study will be approximately 9 months. For participants who continue in the optional extension phase, the duration of the study is up to 27 months.
Study methodology	
This is a single center, dose-escalation study designed to evaluate the safety, and tolerability of maximal dose level of dantrolene sodium administered orally over 6 months with an optional extension phase up to 24 months in patients with Wolfram syndrome.
 
The study will have 'x' periods as follows:
 
 Baseline and confirmatory screening (all patients): within 56 days prior to treatment. Dose maximization period (weeks 0-3 for each patient). Treatment period (weeks 1-) for all patients. Week 0 through week 3 (+/- 2 days): dose escalation up to the maximum recommended. Assessments for safety at months 1 (+/- 2 days), 2 (+/- 7 days), 4 (+/- 7 days), and 6 (+/- 7 days); and clinical examination, including ophthalmic, neurologic, endocrine, and laboratory assessments at months 0 and 6 (+/- 7 days). For participants who continue in the optional extension phase, additional assessments for safety at months 12 (+/- 7 days), 18 (+/- 7 days), and 24 (+/- 7 days); and additional clinical examinations, including ophthalmic, neurologic, endocrine, and laboratory assessments at months 12 (+/- 7 days), 18 (+/- 7 days) and 24 (+/- 7 days). Outcome measure evaluations (all patients): month 6 (+/- 7 days) after the last dantrolene sodium administration for participants who complete the study, month 24 (+/- 7 days) after the last dantrolene sodium administration for participants who complete the optional extension phase, and within 28 days (+/- 7 days) after the last dantrolene sodium

administration for patients who discontinue prior to the end of the study.

- Final Safety Follow-Up (all patients): within 28 days (+/- 7 days) following discontinuation of study drug.

Patient eligibility will be based on a diagnosis of Wolfram syndrome. Eligibility will be confirmed during the baseline screening visit. Patients who have provided written informed consent/assent to participate in this study will undergo baseline screening procedures, which will include a review of the study entry criteria and standard laboratory tests (serum chemistry, hematology and urinalysis), genetic testing confirmation, ophthalmic examination, standardized neurological and endocrinology evaluations. When central apnea is suspected in a participant, baseline screening will include the confirmation of the absence of central apnea based on the result of most recent polysomnography. Patients who are confirmed eligible based on the results of the baseline screening assessments will be enrolled to receive study drug.

Baseline procedures will include complete physical exam, standard clinical laboratory tests (serum chemistry, liver function tests, hematology and urinalysis, bone chemistry), protocol-specific laboratory testing (e.g.), 12 lead ECG. If there are no safety concerns, patients will begin the 3-week dose maximization period of the study drug.

We will perform ECG before and 4 hours after the first dose of dantrolene sodium, then again at months 2 and 6. For participants in the optional extension phase, we will also perform ECG at months 12, 18, and 24.

All patients will undergo outcome measure evaluations at month 6. Participants in the optional extension phase undergo outcome measure evaluations at months 12, 18, and 24.

[figure not shown]
Outcome measure evaluations will include standard clinical laboratory tests (serum chemistry, haematology and urinalysis), 12-lead ECG, vision assessments, neurological examination, remaining beta cell function assessment (boost test), protocol-specific laboratory testing, and standardized functional activities of daily living tests.

A Final Safety Follow-Up visit will be conducted at 28 days (+/- 7 days) after the outcome measure evaluations to collect updated information on adverse events and concomitant medications, therapies and procedures. For patients who discontinue prior to the outcome measure evaluations, this will be conducted within 28 days (+/- 7 days) after the last dantrolene sodium administration.

	
Administration of dantrolene sodium will be contingent upon normal results of the relevant safety laboratory tests and measures (i.e., LFTs).
 
All adverse events, safety lab results and use of concomitant medications will be monitored closely by the PI throughout the study and for 30 days following discontinuation of study medication. If any clinically significant laboratory or clinical abnormality occurs, the subjects will be monitored closely until resolution or clinically stable. Study medication will be discontinued if indicated. Progress of the trial will be determined following periodic reviews by a Data and Safety Monitoring Board (DSMB) of the safety data in all previously enrolled patients.

Statistical Methodology	
The first aim of the statistical analysis will be to assess safety and tolerability of dantrolene sodium in this patient population. The analysis will be based on all enrolled patients and will not include any formal statistical tests. To evaluate safety, the number and percentage experiencing each adverse event will be tabulated and compared by treatment status. Adverse events will be summarized by severity and by category. Vital signs, and serum chemistries, hematology and urinalysis safety monitoring will be listed for each patient and abnormal values will be flagged. The maximum dose received by patients, duration of treatment and reasons for dose reductions or early withdrawal will be reported to assess tolerability of treatment.
 
The second aim of the statistical analysis will be to assess efficacy in terms of the secondary outcome measures of residual beta cell functions, visual acuity, and neurological function. Each variable will be quantified as a change from the baseline value. The trajectory of change for each variable will be assessed between baseline and 6-month assessments. For participants in the optional extension phase, the trajectory of change for each variable will be assessed between baseline, 6-month, 12-month, 18-month, and 24-month assessments..
 
As this is a rare disease and the trial involves only a small numbers of patients, statistical inferences will be based on estimation rather than hypothesis testing. Specifically a Bayesian approach to estimation will be used based on both non-informative and informative priors as appropriate. This type of approach has been endorsed for trials of rare diseases. Drop-outs may be replaced, such that an adequate number of evaluable patients complete the study.

Individual stopping criteria	
1. If a participant experiences more than a few but not more than 10 diarrhea stools in a single day while taking dantrolene sodium, a temporary withdrawal (48 h or longer) should be discussed with a PI. A patient with Wolfram syndrome tends to

	
have diarrhea due to autonomic dysfunction. Thus, the temporary withdrawal is determined by the discretion of the PI. If a patient experiences more than 10 diarrhea stools in a single day, a temporary withdrawal (48 h or longer) should be immediately done. After the temporary withdrawal, a participant should use the previously tolerated dosing regimen.
 
2. If a participant experiences significant muscle weakness while taking dantrolene sodium, a participant should use the previously tolerated dosing regimen. Muscle weakness is examined at every study visit as part of the physical exam. Muscle weakness is assessed by the following methods.
 
 • Rise to stand from floor without using hands. If a participant cannot do this due to neurological dysfunction of Wolfram syndrome, the order in which we would like a participant to attempt is the following: From floor with hands, from a chair without using hands, from a chair with hands. • Hand grip strength using a hand dynamometer, left and right. 
If a participant cannot rise to stand with the method he/she used or a participant's total hand grip strength (sum of right- and left-hand grip strength) is decreased by more than 20% with the current dosing regimen, a patient should use the previously tolerated dosing regimen.
 
Two failures in either of these two steps would constitute stopping the drug permanently.
 
3. ALT or AST >8xUpper Limits of Normal (ULN) 4. ALT or AST >5xULN for more than 2 weeks 5. ALT or AST >3xULN and (serum total bilirubin >2xULN or international normalized ratio >1.5) 6. ALT or AST >3xULN with the appearance of fatigue, nausea, vomiting, right upper quadrant pain or tenderness, fever, rash, and/or eosinophilia (>5%)

Study stopping criteria	We define the study stopping criteria based on established adverse event criteria, the National Cancer Institute (NCI) Common Terminology Criteria for Adverse Events (CTCAE), Version 4. The study may need to be stopped if ≥2 patients on drug develop the same CTCAE Grade 3 or if 1 patient develops a CTCAE Grade 4 or higher.

FIGURE: CLINICAL TRIAL DIAGRAM

For participants who continue in the optional extension phase

**Study Visits 10,
11, and 12
Month 12, 18,
and 24**

Assessment of Clinical Outcome Measures
Discontinue study med or placebo; Complete PE, VS/Wt, all safety labs and evaluative labs: liver enzyme testing (ALT, AST, alkaline phosphatase, bilirubin), Eval labs: blood glucose levels, CBC with differential, comprehensive metabolic panel, proinsulin, C-peptide, HbA1C, myelin basic protein and MANF levels (ELISA), osm, phos, Am, UA(micro/macro, glucose); ECG, beta cell functions, neurological and ophthalmology exam, visual functioning questions, QOL questions.

Final Follow up

Safety labs, AE monitoring, complete PE, VS/Wt

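### The primary safety endpoint includes changes in laboratory tests, but the planned analysis only lists values and flags abnormal ones, so change from the pre-dose value has no planned estimate

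*Combined protocol and SAP*

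**What the plan says.** Under Study endpoints, the synopsis assesses primary safety by adverse events and by "changes in clinical laboratory testing (including liver function tests". The next bullet adds: "This will be assessed by monitoring of serum chemistry including liver function tests and ammonia".

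Under Statistical Methodology, the first aim (safety) handles these tests in one sentence: "Vital signs, and serum chemistries, hematology and urinalysis safety monitoring will be listed for each patient and abnormal values will be flagged". It does not say what counts as abnormal. The same aim rules out formal tests and uses all enrolled patients. The second aim (efficacy) covers beta cell function, visual acuity and neurological function, and there the plan does specify change: "Each variable will be quantified as a change from the baseline value".

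Two other places bear on who can have a raised value before dosing. Exclusion criterion 3 defines abnormal liver function as "serum transaminases more than twice the upper limit of normal for the reference laboratory", so the entry rule admits values up to 2xULN. Study methodology, however, states: "Administration of dantrolene sodium will be contingent upon normal results of the relevant safety laboratory tests and measures (i.e., LFTs". It does not define normal.

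**The concern.** A primary endpoint component is worded as change, yet the only analysis assigned to it classifies each value on its own. The secondary variables get the change analysis that the primary laboratory component lacks.

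This matters more here than in a controlled trial. Study methodology describes a single-centre dose-escalation study and no control arm. The phrase about comparing by treatment status and the stray mention of placebo in the trial diagram do not create one. Without a comparator, only the patient's own pre-dose value can separate a drug effect from the starting level. The plan also says that its inferences rest on estimation, but it names no laboratory safety quantity to estimate. If the summary is left open, it will be chosen after the results are seen.

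**Working it through.** The plan gives no figure for this point, so there is none to reproduce. The check asks whether any reasonable flag limit could stand in for a measure of change.

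**Inputs.** The flag limit is not stated, so two candidates were tried: 1xULN (the ordinary laboratory limit) and 2xULN (the only definition of abnormal liver function in the documents, exclusion criterion 3). The value pairs below are illustrations in multiples of ULN, with baselines inside the entry limit. Ratio = on-drug value / pre-dose value; a value is flagged if it exceeds the limit.

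| Pre-dose to on-drug | Ratio | Flag at 1xULN (before / after) | Flag at 2xULN (before / after) |
|---|---|---|---|
| 1.5 to 1.5 | 1.0 | yes / yes | no / no |
| 1.5 to 2.9 | 1.93 | yes / yes | no / yes |
| 0.3 to 0.9 | 3.0 | no / no | no / no |
| 0.5 to 1.9 | 3.8 | no / yes | no / no |
| 0.5 to 3.1 | 6.2 | no / yes | no / yes |

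At 1xULN, an unchanged 1.5 and a near-doubling to 2.9 give the same pair of flags. At 2xULN, an unchanged 1.5 and a 3.8-fold rise to 1.9 give the same pair. Neither limit measures change. Any value above 2xULN is flagged under both, which covers every ALT or AST level in the individual stopping criteria (above 3xULN and higher).

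**How much drift could stay below the flag.** The documents give no baseline distribution. As an assumption, take log-normal baselines with median m = 0.4 to 0.7xULN and log-SD s = 0.4 to 0.6, truncated at 2xULN. If every patient's value doubles, the share left unflagged at limit L is Φ(ln((L/2)/m)/s) / Φ(ln(2/m)/s).

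- L = 1: lowest at m = 0.7, s = 0.4 (20%); highest at m = 0.4, s = 0.4 (71%).
- L = 2: lowest at m = 0.7, s = 0.6 (75%); highest at m = 0.4, s = 0.4 (99%).

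**What the planned size could deliver.** With all 50 enrolled patients (25 adults, 25 children):

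- The 95% half-width for a mean change is t(0.975, n-1)/√n in SD units: 2.010/√50 = 0.28 SD overall, and 2.064/√25 = 0.41 SD in each age group.
- If no patient worsens, the exact two-sided 95% upper limit is 1 - 0.025^(1/n): 7.1% for n = 50 and 13.7% for n = 25.
- The chance of seeing at least one worsening when the true rate is 5% is 1 - 0.95^n: 92% for n = 50 and 72% for n = 25.

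These figures assume that every enrolled patient has a pre-dose value and at least one on-drug value.

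**The case against.** The strongest defence is that the endpoint is about monitoring, as the second endpoint bullet suggests, and that listing with flags is monitoring. Other safeguards surround it. Adverse events are summarised by severity and category ("the number and percentage experiencing each adverse event will be tabulated and compared by treatment status"), clinically significant laboratory abnormalities are followed up, a safety board reviews the data, and the stopping criteria act on multiples of ULN. In an uncontrolled study of up to 50 patients with no formal safety tests, a summary of drift within or near the normal range could be called a matter of taste.

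Part of this stands. The listings lose no data, a reader can derive change from them, and large rises are not hidden. But the endpoint names laboratory change separately from adverse events, and nothing says which laboratory rises become adverse events. Stopping criteria protect individuals; they do not summarise the cohort.

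Three stronger readings are tempting and are not supported:

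- A reader might infer that the flag will mark unchanged patients as affected, because entry allows up to 2xULN. That needs a 1xULN flag, which the plan does not state, and it needs such patients to be dosed, which the requirement for normal results puts in doubt.
- A reader might infer that real liver signals would be missed. That is shown only for rises that end at or below the flag limit.
- A reader might extend the point to glucose. Blood and urine glucose belong to the beta cell measures, and the second aim analyses beta cell function as change.

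**Conclusion.** The point holds in a limited form. The stated analysis does not estimate the laboratory part of the primary endpoint as worded, and no choice of flag limit repairs that. What is lost is a pre-planned summary, chiefly of a cohort-wide drift below the limit; neither data nor detection of rises above 2xULN (at the two limits tried) is lost.

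The mismatch itself rests on the text alone. The unflagged shares (20% to 71% at 1xULN, 75% to 99% at 2xULN) depend on assumed baselines and a uniform doubling, and only illustrate scale. The documents do not say how many patients would enter between 1 and 2xULN. The change should be made before the data are analysed; it does not call the design into question.

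**What to change.** In Statistical Methodology, first aim:

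1. For ALT, AST, bilirubin, alkaline phosphatase and ammonia, report change (or ratio) from the last pre-dose value at each visit where the test is measured, with a confidence or credible interval.
2. For ALT and AST, add a shift table of pre-dose category against worst on-drug category, using the multiples of ULN already in the exclusion and individual stopping criteria (up to 1, >1 to 2, >2 to 3, >3 to 5, >5 to 8, >8). Give the proportion who worsen with an exact confidence interval. Limit this table to ALT and AST: the documents give no cut-points for alkaline phosphatase or ammonia, and only one for bilirubin. The change summary in item 1 is still needed, because a rise from 0.3 to 0.9xULN stays in the lowest category.
3. State the flag limit, and mark each flagged value as present before dosing or new on drug. Do not remove existing flags: restricting them to a worsened category would drop a rise from 1.1 to 1.9xULN.
4. Keep the patient listings as support.

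Separately, exclusion criterion 3 (entry up to 2xULN) and the Study methodology statement that dosing depends on normal liver tests must be reconciled.

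The cost is some wording and a few extra tables. No new data, visits or patients are needed.

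### Does a target of 46 evaluable patients (23 adults and 23 children) fail to follow from 50 enrolled at 10% drop-out?

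*Combined protocol and SAP*

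**What the plan says.** The synopsis row on the number of patients planned states: "Up to 50 patients (25 adults and 25 children) will be enrolled to provide a total of" a certain number of completers. That number is given as "46 evaluable patients who complete the study (23 adults and 23 children), based on an anticipated drop-out rate of 10" per cent. Enrolment and completers are thus both broken down by age group.

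The Statistical Methodology row adds: "Drop-outs may be replaced, such that an adequate number of evaluable patients complete the study". It gives no number for what is adequate. The same row bases the safety analysis on all enrolled patients without formal tests. For the trial's inference in general it says that "statistical inferences will be based on estimation rather than hypothesis testing", using a Bayesian approach.

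**The concern.** The row gives three figures that a reader will multiply together at once: 50 enrolled, 10% lost, 46 left. The product is 45. Read the other way, 46 of 50 is a loss of 8%. To expect at least 23 completers in a group at 10% loss, one would enrol 26 per group, or 52 in all, which is above the ceiling of 50.

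These are the only figures on sample size in the text supplied. If 46 were the number that decides whether enough patients have completed, and so whether drop-outs are replaced, an overstated target could matter in practice. The trial would fall short of it more often than not with drop-out exactly as assumed, and it would have no places left under the ceiling to make up the loss.

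**Working it through.** **Inputs.** From the row on number of patients planned: 25 adults and 25 children enrolled (50), 23 and 23 evaluable (46), drop-out 10%. From the Statistical Methodology row: replacement permitted; estimation, not testing.

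**1. The plan's own figure, by age group.** Completers per group = enrolled × (1 − drop-out) = 25 × 0.90 = 22.5. Rounded half up to a whole patient this is 23, and 23 + 23 = 46. Both the group figures and the total are reproduced exactly.

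**2. The total without rounding.** 50 × 0.90 = 45. The difference is 46 − 45 = 1 patient, and 1/45 = 2.2%. Per group it is 23 − 22.5 = 0.5 patient.

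**3. What whole patients allow.** No whole number of drop-outs in a group of 25 is exactly 10%. Two is 2/25 = 8% and three is 3/25 = 12%, equally far from 10%. Nor can 45 be split equally between two groups. A plan with equal groups must state 22 + 22 = 44 or 23 + 23 = 46, and each is one patient from 45. The implied 8% therefore reflects rounding in groups of 25 and is not a second, conflicting drop-out assumption.

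**4. Backwards.** 23/0.90 = 25.6, so 26 per group and 52 in total if 23 must be the least number expected. 22.5/0.90 = 25 exactly. The enrolment of 25 per group is what an expected 22.5 requires. The extra patient per group is needed only if 23 is read as a floor for the expectation, and the plan does not say that it is.

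**5. Chance of reaching the figure.** Assume independent drop-out at 10% and no replacement.

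| Event | Probability |
|---|---|
| At least 46 of 50 complete | 43.1% |
| At least 45 of 50 complete | 61.6% |
| At least 23 of 25 complete, one group | 53.7% |
| At least 23 of 25 complete, both groups | 0.537² = 28.8% |

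Even the exact expectation of 45 is missed in 100 − 61.6 = 38.4% of cases. A figure near the expected count is often missed, so a large chance of missing 46 does not show an arithmetic error. These probabilities also leave out replacement, which the plan permits.

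**6. What depends on 46 rather than 45.** The denominator for safety is the number enrolled, so it does not change. For efficacy, interval width goes roughly as 1/√n if a non-informative prior is used. √(46/45) = 1.011, a difference of about 1% in width. No power calculation, precision target or replacement trigger in the plan refers to 46.

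**The case for a change.** The strongest case is this. The row states a total, and the total needs no rounding, because 10% of 50 is exactly 5. Rounding up twice before adding creates the extra patient, in the favourable direction, and the documents never say that this was done. Since 46 is the only evaluable count given, it is the natural reading of an adequate number in the replacement rule. With all 50 places filled and 5 patients lost, the trial would be one short, and nothing says whether a 51st patient may then be enrolled.

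Part of this stands. The rounding is inferred, it is favourable, and the plan does not say whether replacements count within the 50.

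The rest does not. The total is presented with its two group figures, and it is their sum. The replacement rule does not name 46 and sets no trigger, so that link is the reader's. The ceiling and the replacement rule are both permissive, and they are compatible: a drop-out can be replaced while enrolment is below 50. The silence on a 51st patient is a missing detail, and it would be there whether the row said 45 or 46.

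**Conclusion.** The concern does not hold. The stated 46 is 22.5 per age group rounded to 23 and doubled. It differs from the unrounded 45 by one patient in total, within the rounding of an approximate planning assumption. Changing it to 45, or the drop-out rate to 8%, would alter no analysis set, test or conclusion, and would change the width of an efficacy interval by about 1%.

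This rests on three things: that the figures were rounded half up within each age group, which fits exactly but is not stated; that 23 per group is an expected count and not a guaranteed minimum; and that no power or precision target is tied to 46, which is true of the text supplied, largely a synopsis.

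### Does making dosing contingent on normal liver tests, with no limit or time point given, clash with the entry and stopping limits?

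*Combined protocol and SAP*

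**What the plan says.** Liver tests enter the protocol synopsis at four points.

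- **Eligibility.** Exclusion criterion 3 bars patients with abnormal liver function, "defined as serum transaminases more than twice the upper limit of normal for the reference laboratory". Under Study methodology, "Patients who are confirmed eligible based on the results of the baseline screening assessments will be enrolled to receive study drug".
- **Before the first dose.** Baseline procedures include "standard clinical laboratory tests (serum chemistry, liver function tests, hematology and urinalysis, bone chemistry". Then: "If there are no safety concerns, patients will begin the 3-week dose maximization period of the study drug". No liver-test limit is attached to this check.
- **The dosing condition.** Later in Study methodology: "Administration of dantrolene sodium will be contingent upon normal results of the relevant safety laboratory tests and measures (i.e., LFTs". The next paragraph provides for close monitoring by the investigator, follow-up of significant abnormalities until they resolve or stabilise, and periodic review by the data and safety monitoring board. It adds: "Study medication will be discontinued if indicated".
- **Stopping.** Items 3 to 6 of the Individual stopping criteria are liver rules: ALT or AST above 8×ULN; above 5×ULN lasting beyond 2 weeks; above 3×ULN with bilirubin above 2×ULN or INR above 1.5; and above 3×ULN with listed symptoms or eosinophilia above 5%.

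Item 1 of the same criteria, on diarrhea, is more explicit about interruption: "If a patient experiences more than 10 diarrhea stools in a single day, a temporary withdrawal (48 h or longer) should be immediately done", followed by "After the temporary withdrawal, a participant should use the previously tolerated dosing regimen". No equivalent text for liver tests appears in the available document.

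**The concern.** The dosing condition is worded as mandatory, but its key word is undefined. Three things look wrong.

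First, *normal* ordinarily means within the reference range. On that meaning, a patient whose transaminases are above 1× and up to 2×ULN is eligible and enrolled, yet may not be dosed.

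Second, if the condition runs throughout treatment, a moderate rise would bar dosing well before any stopping criterion is met. Nothing liver-specific says whether to hold, when to resume, or at what regimen.

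Third, the tests covered are not listed. Exclusion criterion 3 speaks only of transaminases, whereas the Month 12, 18 and 24 box of the trial diagram lists ALT, AST, alkaline phosphatase and bilirubin as the liver tests.

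The primary endpoint is safety and tolerability, with liver tests named in it. Tolerability is to be reported through maximum dose, duration of treatment, and reasons for dose reduction or early withdrawal. If the same liver value could lead to continuing, holding or stopping, those summaries would partly reflect how one word was read.

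**Working it through.** The plan gives no figure to reproduce, so the check is one of consistency between thresholds. Let *x* be ALT or AST as a multiple of ULN.

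Inputs:

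- Eligible if *x* ≤ 2 (Exclusion criteria, item 3).
- Dosing condition met if *x* ≤ 1 (reading A, within the reference range) or *x* ≤ 2 (reading B, the complement of the definition in exclusion criterion 3). Both readings are assumptions, because the sentence gives no limit.
- Liver stop if *x* > 8; or *x* > 5 beyond 2 weeks; or *x* > 3 with a bilirubin, INR, symptom or eosinophilia finding (Individual stopping criteria, items 3 to 6).

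| *x* (×ULN) | Eligible at entry | Meets condition, A | Meets condition, B | Stop: no added finding, up to 2 weeks | Stop: no added finding, beyond 2 weeks | Stop: with added finding |
|---|---|---|---|---|---|---|
| up to 1 | yes | yes | yes | no | no | no |
| >1 to 2 | yes | no | yes | no | no | no |
| >2 to 3 | no | no | no | no | no | no |
| >3 to 5 | no | no | no | no | no | yes |
| >5 to 8 | no | no | no | no | yes | yes |
| >8 | no | no | no | yes | yes | yes |

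**At entry.** Reading A leaves one band, above 1× and up to 2×ULN, that is eligible but fails the dosing condition. Reading B leaves none for transaminases.

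**On treatment, if the condition applies throughout.** The band that fails the condition without any liver stop, whatever the other findings, is >1 to 3 on A and >2 to 3 on B. The two overlap in >2 to 3. With no added finding, the upper end moves to 5×ULN for elevations lasting beyond 2 weeks and to 8×ULN for shorter ones.

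**On treatment, if the condition applies only before the first dose.** No such band exists, because the stopping criteria alone govern later values.

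The next question is whether any cell is a contradiction, meaning two instructions that cannot both be followed. None is. Exclusion criterion 3 decides who may enrol, and it does not order dosing. The baseline text puts liver tests and a safety check between enrolment and the first dose, so a further condition there can be obeyed without breaching the eligibility rule. During treatment, a condition for giving drug can sit alongside less strict criteria for stopping it permanently. What the table shows is a set of bands in which the plan does not spell out the action.

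**The case for a change.** The strongest case for a change is that the sentence speaks of giving the drug in general, not of starting it, and stands directly before text about monitoring throughout the study. A continuing condition is therefore a reasonable reading. On that reading the band above 2× and up to 3×ULN remains open under either meaning of *normal*. Borrowing the entry definition does not help for alkaline phosphatase or bilirubin. Monitoring and flagged listings reveal the values but do not say which rule was to be followed. The plan states an interruption rule for diarrhea, so it could state one for liver tests, and the clarification itself would add no patients and no analyses.

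Much of this stands as description: the term is undefined, the scope is unstated, and the threshold bands are correct. It does not establish a defect.

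- Placement is weak evidence of scope. A continuing bar on any value above 1× or 2×ULN would leave graded criteria such as the 5×ULN, 2-week rule little practical work. A pre-dose condition followed by the stopping criteria gives every sentence a role.
- Diarrhea of up to 10 stools a day is also left to the investigator's discretion, so judgement below a hard limit is how this plan works elsewhere.
- The absence of a liver hold rule can be asserted only of the available text, which is headed as a synopsis, has a figure missing, and shows only the later visits of the trial diagram.

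**Conclusion.** No change to the plan follows. This is missing detail that a single-centre investigator can handle with the stopping criteria, close monitoring, the general provision for discontinuation, board review, and the study-level stopping criteria based on CTCAE grades.

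The effect on the analysis is limited. Statistical Methodology describes safety in all enrolled patients without formal tests, lists laboratory values by patient with abnormal ones flagged, and reports maximum dose, treatment duration, and reasons for dose reduction or early withdrawal. A reader can therefore see the values and much of the dosing outcome. A temporary hold is not named among the reported items, so that part would be less visible. At entry the stricter reading withholds drug, so it adds no exposure.

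The size is bounded only in thresholds: above 1× and up to 2×ULN at entry on the stricter reading, and at least above 2× and up to 3×ULN on treatment if the condition is continuous. The rule applies to up to 50 patients, but the documents give no basis for estimating how many would fall in either band.

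The conclusion rests on reading the entry rule, the baseline check and the dosing condition as successive steps, which the text permits but does not state. If the sponsor reconciles these passages in the course of other edits, the meaning and scope of the condition are for the sponsor and the board to settle. This review takes no view on which limit or action is clinically right.
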